#### 4.2 Arms and Interventions

Arms: Participants having a harvested total "Adipose Derived Stem Cell (ADSC)" count (in 5 ml SVF solution) between 1 x 10^6 to 2 x 10^6 will be placed in "Group A".

Participants having a harvested total "Adipose Derived Stem Cell (ADSC)" count (in 5 ml SVF solution) more than  $2 \times 10^6$  will be placed in "Group B".

Interventions: Both group A and Group B will be injected intravenously with harvested 5 ml of SVF containing Autologous Non Expanded ADSC and outcome will be observed over the period of 1(one) year.

#### 4.3 Study duration

From April 2019 Onwards (Approximately Five years / Till completion of sample requirements with minimum one year of follow up).

#### 4.5 Study population:

Patient of CKD who fulfill the selection criteria and admitted at the selected health facility for treatment.

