#### 4.7 Sampling technique & Recruitment of study subjects

Participants of the study will be recruited from the patients with CKD attending the Bangladesh Laser & Cell Surgery Institute & Hospital considering the eligibility criteria. The recruitment will be continued till the desired sample is drawn.

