#### 4.8 Eligibility criteria

#### 4.8.1 Inclusion criteria

A patient is eligible for the study if all of the followings apply:

- a) Aged 18-80 years (inclusive)
- b) With chronic kidney disease (CKD)stage 3 to 5 (eGFR 60 to 0 mL/min/1.73m2 (inclusive)) Note: eGFR = estimated glomerular filtration rate
- c) Having provided informed written consent.

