#### 4.8.2 Exclusion criteria

Any patient meeting any of the exclusion criteria will be excluded from study participation.

- 1) Known hypersensitivity to any component used in the study.
- 2) With inadequate hematologic function with: absolute neutrophil count (ANC) <1,500/μL OR platelets < 100,000/μL OR Hemoglobin < 8 g/dL
- 3) With impaired hepatic function with: serum bilirubin, aspartate aminotransferase (AST), alanine aminotransferase (ALT) or alkaline phosphatase (AKP), prothrombin time above and normal reference and serum albumin below normal reference range.
- 4) With hemoglobin A1c (HbA1c) > 8.0%
- 5) With serious prior or ongoing medical conditions (e.g. concomitant illness such as cardiovascular (e.g. New York Heart Association grade III or IV), hepatic e.g. Child-Pugh Class C), psychiatric condition, alcoholism, drug abuse), medical history, physical findings, ECG findings, or laboratory abnormality that in the investigators' opinion could interfere with the results of the trial or adversely effect the safety of the patient

- 6) Pregnant or lactating women or premenopausal with childbearing potential but not taking reliable contraceptive method(s) during the study period
- 7) With known history of human immunodeficiency virus (HIV) infection or any type of hepatitis
- 8) Judged to be not applicable to this study by investigator such as difficulty of followup observation
- 9) With any other serious diseases/medical history considered by the investigator not in the condition to enter the trial
- 10) Known or suspected abuse of alcohol or narcotics
- 11) With known history of cancer within past 5 years
- 12) With any autoimmune disease
- 13) With congenital kidney disease
- 14) With precancerous condition or with raised tumour markers like Alpha feto protein, Carcino embryonic antigen (CEA), C.A 19.9, C.A 125, Serum PSA above normal reference range.
- 15) Participants having a harvested total "Adipose Derived Stem Cell (ADSC)" count (in 5 ml SVF solution) less than 1 x 10^6 will be excluded from the study.

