#### 4.13 Data collection procedure:

Current study involves collection of both primary and secondary data. Primary data will be collected by face to face interview of the patients or patient's attendant by the researcher at health facility during the period of hospital stay, upon their consent and convenience. Socio demographic and personal information will be recorded from patient through interview, with a semi structured pre-tested questionnaire. Information regarding risk factors and risk behavior will be inquired taking effort to minimize the recall bias.

Secondary data about present state and diagnosis will be collected from hospital record as well as from treatment sheet. For acquiring secondary data a structured checklist will be used.

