#### 6.3 Materials

- **a) Study population** According to sample size calculation 31 patients with established CKD will be recruited in the study over the estimated study period.
- **b) Equipment** "UNISTATIONTM" a specially designed medical device to satisfy diverse demands for various autologous cell therapies.

UNISTATION is a specially designed medical device to satisfy diverse demands for various autologous cell therapies with only one device. PRP, PRF isolation, and fat purification functions have been added to UNISTATIONTM.

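### CKD is required at entry but no test of chronicity or stability is set, so recovery from an acute-on-chronic fall could be read as an SVF effect

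*Combined protocol and SAP*

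**What the plan says.** Section 4.5 describes the population as "Patient of CKD who fulfill the selection criteria and admitted at the selected health facility for treatment". Section 4.7 uses a broader phrase: participants are "recruited from the patients with CKD attending the Bangladesh Laser & Cell Surgery Institute & Hospital".

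The only renal entry criterion is 4.8.1(b): "With chronic kidney disease (CKD)stage 3 to 5 (eGFR 60 to 0 mL/min/1.73m2 (inclusive"). It names chronic disease and gives a staging range, but no second value, minimum duration or stability window. Section 6.3 adds that "31 patients with established CKD will be recruited in the study" and does not define established.

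Section 4.8.2 lists 15 exclusions. None names acute kidney injury, acute-on-chronic decline, a recent change in eGFR, or newly started dialysis. The nearest are items 5, 8 and 9, which leave the decision to the investigator. Item 5, for example, covers conditions or laboratory abnormalities that in the investigators' opinion "could interfere with the results of the trial or adversely effect the safety of the patient".

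All participants receive SVF (4.2, 4.9). The efficacy primaries in 4.11.1 are changes from baseline to week 24 in renogram GFR (b), creatinine-based eGFR in stage 4 and below (c), and dialysis score in stage 5 (d). Annexure D has one pre-treatment visit, at week 0.

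**The concern.** A patient with CKD whose function has dropped for a temporary reason still has CKD and still falls in the eGFR range, so that patient qualifies under the plan as written. The lowered value then becomes the week-0 baseline. If function recovers by week 24 without any help from SVF, the gain appears in (b) and (c). If dialysis had been started for the episode and then stops, the change appears in (d). With no untreated comparator and no earlier renal value, nothing in the data would separate this from a treatment effect.

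At stake is objective (iii) in 3.2, whether SVF reverses or limits progression. The point is about who enters. It is related to the missing control but separate from it, because entry criteria can reduce this bias even if the sponsor keeps the present design.

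**Working it through.** **The plan's own figure.** Section 4.6 uses two-sided alpha 0.05, beta 0.20, E = 0.5 and an SD of change of 1.0: N = (1.960 + 0.842)² / (0.5/1.0)² = 7.849 / 0.250 = 31.4, stated as 31. This is the one-sample, before-after form. A two-group comparison at the same effect would need 63 per group. The trial is therefore sized to test change from baseline, which is the test used below.

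**Inputs not in the documents.** The plan gives no share of unstable entrants, no size of recovery, no SD of change in mL/min and no background decline. All four are assumed and varied:

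- f = share of entrants who recover: 10%, 20%, 30%
- R = size of recovery: 5 or 10 mL/min
- σ = SD of the 24-week change in the absence of recovery: 6 or 10 mL/min
- d = background decline over 24 weeks: 0 or 1 mL/min

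**Formulae.** With no true SVF effect, the mean change is μ = fR − d and the SD of change in the mixed group is s = √(σ² + f(1−f)R²). The expected test statistic is about μ√31/s.

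Worked case, f = 20%, R = 10, σ = 6, d = 0: μ = 0.2 × 10 = 2; s = √(36 + 0.16 × 100) = √52 = 7.21; statistic = 2 × 5.57/7.21 = 1.54. By the normal approximation, the chance of exceeding 1.96 is P(Z > 0.42), about 34%. Simulation with the one-sample t test gives 31%.

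**Chance of a significant rise, n = 31, by simulation** (nominal 2.5% in that direction; mean change in mL/min in brackets):

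| R, σ, d | f = 10% | f = 20% | f = 30% |
|---|---|---|---|
| 10, 6, 0 | 12% (+1) | 31% (+2) | 57% (+3) |
| 5, 6, 0 | 6% (+0.5) | 13% (+1) | 24% (+1.5) |
| 10, 10, 0 | 7% (+1) | 16% (+2) | 31% (+3) |
| 10, 6, 1 | 2% (0) | 11% (+1) | 28% (+2) |

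Runs of the last row differ by about one percentage point (10% to 11%, 28% to 29%). At σ = 6 the planned effect of 0.5 SD is 3 mL/min, the same as the shift from 30% recovering by 10 mL/min.

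**Primary (c)** excludes stage 5. If 10 of the 31 were stage 5 (assumed), n = 21 and the first row becomes about 9%, 21% and 40%.

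**Primary (d).** With the same assumed 10 stage 5 patients, one moving from score 7 to score 0 shifts the mean by 7/10 = 0.7 points.

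**Could it be found afterwards?** Questionnaire 1 records vomiting, loose motion, fever, urine output and dehydration, and Questionnaire 2 records antibiotics and analgesics, but nothing defers or excludes a patient because of them. Neither questionnaire, nor the week-0 sheet, shows a field for CKD duration, an earlier creatinine or the date dialysis began. Section 4.13 says "Secondary data about present state and diagnosis will be collected from hospital record", which does not promise past values.

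**The case against.** A reader might infer that the trial recruits from acute admissions. The documents do not say so. Section 4.7 says attending, the site is a laser and cell surgery institute, 6.1 describes its operating theatre and post-operative care, and admission in 4.5 may simply be for the SVF procedure. This objection stands: the source of patients is unclear, not shown to be acute.

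A reader might also infer that chronicity is not required at all. It is required by name in 4.8.1(b) and 6.3. What is missing is an operational test, and the name alone does not exclude an acute-on-chronic fall.

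Existing exclusions would remove some acutely ill patients: item 2 (neutrophils, platelets, haemoglobin), item 3 (liver tests, prothrombin time, albumin) and the discretionary items. This stands in part. None is a rule about renal stability, and discretion may be applied differently from patient to patient.

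Nor does the bias have to favour SVF. A patient still declining at week 0 would push the other way, and background progression offsets recovery. With an assumed decline of 2 mL/min (R = 10, σ = 6) the chances fall to about 0.3%, 2% and 10%. This stands against any single headline figure. However, the shift fR in the mean is the same whatever the decline: in the last row of the table, 10% recovering exactly cancels a true decline of 1 mL/min, which would look like halted progression.

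Finally, a concurrent control would deal with this more fully. That is so, but it is not a reason to leave the entry criterion undefined.

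**Conclusion.** The concern holds as a gap in the entry criteria. Chronicity and stability are not operationally defined, no listed exclusion covers recent acute kidney injury or dialysis begun for an acute episode, and the design cannot tell spontaneous recovery from an SVF effect in primaries (b), (c) and (d). It would be too strong to say that such recovery will be counted, because that depends on such patients enrolling and on their being at a low point at week 0. The documents establish neither.

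The size is unknown. Across the four tabulated settings the chance of a false significant rise runs from about 2% to 57% against a nominal 2.5%, resting entirely on the assumed share, recovery, SD and decline. It is material if a fifth or more of entrants recover by 10 mL/min with little background decline, and small if few recover or decline is marked.

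**What to change.** Amend 4.8.1(b) to require eGFR in the stage 3 to 5 range on two values at least 3 months apart, with the latest pre-treatment values agreeing within a tolerance that the sponsor states in advance. Take the earlier value from hospital and laboratory records where it exists, and otherwise from a repeat creatinine before entry. Add to 4.8.2 an exclusion for acute kidney injury, or dialysis begun for an acute episode, within that window. Reconcile 4.5 with 4.7 on admitted or attending, and say what the admission is for.

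The cost is a protocol amendment, somewhat slower recruitment, and a wait with one more blood test for patients without an earlier value. The sample-size formula does not change. The amendment reduces the bias but does not let the design detect what remains; that would need a concurrent control.

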#### 4.6 Sample size determination:

 $\alpha$  (two-tailed) = Threshold probability for rejecting the null hypothesis. Type I error rate.

 $\beta$  = Probability of failing to reject the null hypothesis under the alternative hypothesis. Type II error rate.

E = Effect size

 $S(\Delta)$  = Standard Deviation of the change in the outcome.

Here,  $\alpha = 0.05$ 

 $\beta = 0.20$ 

E = 0.5

 $S(\Delta) = 1.0$ 

The standard normal deviate for  $\alpha = Z_{\alpha} = 1.960$ 

The standard normal deviate for  $\beta = Z_{\beta} = 0.842$ 

A = 1.000

$$B = (Z_{\alpha} + Z_{\beta})^2 = 7.849$$

$$C = (E/S(\Delta))^2 = 0.250$$

Sample size N = AB/C = 31 (approx.)

#### 4.7 Sampling technique & Recruitment of study subjects

Participants of the study will be recruited from the patients with CKD attending the Bangladesh Laser & Cell Surgery Institute & Hospital considering the eligibility criteria. The recruitment will be continued till the desired sample is drawn.

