#### 2.6 Clinical trials using mesenchymal stem cells for renal repair

Few clinical trials have tested safety and efficacy of MSCs for renal disease. Reinders and colleagues studied safety and feasibility in six kidney allograft recipients who received two intravenous infusions of expanded autologous bone marrow-derived MSCs [21]. Importantly, delivery of autologous MSCs was not associated with adverse events, nor did it compromise graft survival. Several clinical trials are currently underway to evaluate the therapeutic potential of autologous and allogeneic MSCs for treatment of renal diseases [22] Administration of both bmMSC and adMSC has demonstrated significant reno-protective effects including reduction of intrarenal inflammatory infiltrate, decreased fibrosis, and glomerulosclerosis [12]

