#### 2.8 Route of delivery

Various routes for delivery of ADSCs, ADSC-induced cells, or ADSCs combined with compound materials have been developed for the treatment of different diseases or damaged tissue. These routes can be classified into two categories: systemic delivery through blood vessels (intravenous injection or intra-arterial injection) or local delivery directly into injured tissues or organs [32].

The route of MSC delivery may influence the cells' capacity to home and engraft the damaged tissue, and thereby their efficacy for renal repair. Commonly used experimental methods to deliver MSCs include systemic intravenous, intra-arterial, or intra-parenchymal delivery. In nonhuman primates the cells distribute broadly into the kidneys, skin, lung, thymus, and liver with estimated levels of engraftment ranging from 0.1 to 2.7% [33].

The route of MSC delivery, intravenous, intra-arterial, or intra-parenchymal, may affect their efficiency for kidney repair. When labeled MSC intravenously infused into baboons were observed for 9-21 months, estimated levels of engraftment in the kidney, lung, liver, thymus, and skin ranged from 0.1-2.7% [33] Indeed, the intravenous route lags in delivery efficiency, because MSC may initially be trapped in the lungs[34] Intra-arterial infusion of MSC was the most effective route to achieve immunomodulation in rat kidney transplantation, possibly by avoiding lodging in the pulmonary circulation, allowing MSC to home to the injured kidney [35].

An important feature of MSCs is their capacity to induce proliferation of renal glomerular and tubular cells, increasing cellular survival. By secreting proangiogenic and trophic factors, injected MSCs not only can enhance proliferation, but also can decrease apoptosis of tubular cells [36]. Several routes of administration (intra-parenchymal, sub-capsular, intravenous) have

been explored and all seem to be effective. Multiple, repeated injections of MSCs appear to be even more effective than single injections [37,38].

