4.1 Study design

Study Type: Interventional.

Primary Purpose: Treatment

Study Phase: Phase 1/Phase 2

Interventional Study Model: Parallel Assignment

Participants will be placed in either of the 2 groups, depending on

the number of harvested total stem cell count.

Those having a harvested total "Adipose Derived Stem Cell

(ADSC)" count (in 5 ml SVF solution) between 1 x 10^6 to 2 x

10^6 will be placed in "Group A".

13

Those having a harvested total "Adipose Derived Stem Cell (ADSC)" count (in 5 ml SVF solution) more than 2 x 10^6 will be placed in "Group B".

Both groups will be studied for Phase I/ Phase II trial by the proposed outcome measures over the stipulated time frame.

Those having a harvested total "Adipose Derived Stem Cell (ADSC)" count (in 5 ml SVF solution) less than 1 x 10^6 will be excluded from the study.

Number of Arms: 2

Masking: Triple (Participant, Care Provider, Outcomes Assessor)

Allocation: Non-Randomized

Enrollment: 31 [Anticipated]

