#### 4.11 Outcome measures

#### **4.11.1 Primary Outcome Measure**

a) Incidence of minor adverse events (MAEs), serious adverse events (SAEs) which may be immediate, early or late - for Phase I [Time Frame: Week 48]

Minor adverse events (MAEs):

i) Pain from lipo-suction > 7 days (Early)

- ii) Fever > 7 days (Early)
- iii) Subcutaneous hematoma / abscess formation (Early)
- iv) Allergic reaction (Immediate)

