#### Serious adverse events (SAEs)

- i) Anaphylaxis (Immediate)
- ii) Pulmonary embolism or infarction (Immediate)
- iii) Outset of any neoplastic change (Late)
- iv) Outset of new Cardiovascular events (Late)
- v) Outset of new Cerebrovascular or neurological events (Late)
- vi) Reactivation of treated tuberculosis (Late)
- b) Change from baseline to 24 week visit in estimated glomerular filtration rate (eGFR) and split renal function in all patients for Phase II [Time Frame: Weeks 0, 24]
  - eGFR with split renal function will be evaluated using DTPA Renogram.
- c) Change from baseline to 24 week visit in estimated glomerular filtration rate (eGFR) with serum creatinine level in patients with CKD 4 and below for Phase II [Time Frame: Weeks 0, 2, 4, 12, 24]
  - eGFR will be calculated by Serum Creatinine level using MRDR formula during all visits.
- d) Change from baseline to 24 week visit in need for dialysis in patients with CKD 5 for phase II [Time Frame: Weeks 0, 2, 4, 12, 24]

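### No written step holds the next infusion after an immediate serious adverse event while the 31 patients are recruited

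*Combined protocol and SAP*

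**What the plan says.** Section 4.1 describes a non-randomized Phase 1/Phase 2 trial with 31 patients anticipated, and runs the two phases in the same two groups: "Both groups will be studied for Phase I/ Phase II trial by the proposed outcome measures over the stipulated time frame". Section 4.2 gives every patient in both groups 5 ml of SVF intravenously.

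On recruitment, section 4.7 states "The recruitment will be continued till the desired sample is drawn", and section 6.3 adds that "31 patients with established CKD will be recruited in the study over the estimated study period". Section 4.3 allows about five years, or until the sample is complete with at least one year of follow-up.

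Section 4.11.1(a) makes adverse events the Phase I primary outcome, with a Week 48 time frame. Two serious events carry the label immediate: anaphylaxis, and pulmonary embolism or infarction. The label is given no time window.

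The sections where a safety hold might be expected are outcomes (4.11), data handling and analysis (4.12 to 4.16), ethics (5) and procedure (7). None contains a review, pause or stopping rule. The safeguards that do appear are the exclusions in 4.8.2, the 80-90% cell viability condition in section 7, and the visit forms in Annexures C and D. Section 4.4 and the consent annexure are not in the visible text.

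**The concern.** The trial is an early one, safety is a primary outcome, and the plan itself names two acute, possibly fatal events. Yet the only condition it states for ending recruitment is that the sample is complete. If one patient has an anaphylaxis or an embolism, the visible text does not require anyone to look at that event before the next patient is infused, or to record why dosing went on.

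The safeguards listed above do not cover this. Eligibility and viability checks come before a patient's own injection, and the visit forms collect data afterwards. None of them links one patient's event to the next patient's infusion. What is at stake is the protection of later participants, and a clear record of the decision to continue. The efficacy analysis is not affected.

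**Working it through.** **The plan's own figure.** Section 4.6 uses Z values of 1.960 and 0.842, E = 0.5 and S(Δ) = 1.0. It obtains 7.849 / 0.250 = 31.4, given as 31 (approx.). This reproduces. The sample size is an input here and is not in dispute.

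**Event rate.** The documents give none. Section 2.6 offers one human safety result with a patient count: six kidney allograft recipients given an expanded bone-marrow product, of whom it says "delivery of autologous MSCs was not associated with adverse events, nor did it compromise graft survival". Zero events in 6 patients has a one-sided exact 95% upper limit of 1 − 0.05^(1/6) = 0.393, or 39%. So few patients, given a different product, cannot fix the rate. The rates below are assumptions.

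**Model.** N = 31, independent events with probability p per patient, and each event recognised before the next infusion.

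- Chance of at least one event: P1 = 1 − (1 − p)^31.
- Mean number infused up to and including the first event (31 if none): M1 = P1 / p.
- Mean number still to be infused, given that a first event occurs: (31 − M1) / P1.
- Chance of a second event: P2 = 1 − (1 − p)^31 − 31p(1 − p)^30.
- Mean number of infusions deferred by a pause at the second event: 31 − Σ P(X_k ≤ 1) over k = 0 to 30, where X_k is the number of events in the first k patients.

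| Assumed p | P1 | M1 | Still to be infused after a first event | P2 | Deferred by a second-event pause |
|---|---|---|---|---|---|
| 1% | 0.268 | 26.77 | 15.8 | 0.038 | 31 − 30.61 = 0.39 |
| 2% | 0.465 | 23.27 | 16.6 | 0.127 | 31 − 29.63 = 1.37 |
| 5% | 0.796 | 15.92 | 18.9 | 0.463 | 31 − 25.19 = 5.81 |

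Worked for 2%: 0.98^31 = 0.535, so P1 = 0.465. M1 = 0.4654 / 0.02 = 23.27. Then (31 − 23.27) / 0.4654 = 16.6.

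**Reading.** P1 is also the chance that the proposed hold is triggered, so it measures the rule's burden as well as its reach. If all 31 are infused, the expected number of events is 31p = 0.31, 0.62 and 1.55. Even at 1% to 2%, a first event, if it happens, would on average leave about half the sample still to be treated. A pause at the second event adds little at those rates.

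**The case against.** The strongest reply is that section 4.7 is about sampling. It says where patients come from and when sampling ends; it does not order infusions to go on after a serious event. That stands. A reader might infer that the plan forbids a pause, or that the trial has no safety oversight. The documents support neither: the text is silent, and some pages are not visible.

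Pace also matters. Section 4.7 names one hospital, and each product is made from the patient's own fat. If accrual is even over about four years (five less one of follow-up, an assumption), 31 patients means one about every 47 days (4 × 365 / 31). The same team would then probably know of an acute event before the next infusion. This makes the practical gap smaller but does not close it, because section 4.3 does not fix the spacing and being aware of an event is not a required review.

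Three other inferences go beyond the documents:

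- **That these events are always known on the infusion day.** The immediate label has no window, the first scheduled visit after treatment is at week 2, and the later forms list no lung imaging. An infarction could be recognised later.
- **That decisions to continue would go unrecorded.** Serious events are a primary outcome, and the all-visit form in Annexure C asks about chest pain and respiratory distress. The text simply does not require that the decision be documented.
- **That section 2.8 concedes an embolism risk.** Its words are "the intravenous route lags in delivery efficiency, because MSC may initially be trapped in the lungs", which concern delivery to the kidney. Section 2.7 also cites clinical studies as indicating safety.

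Finally, the rates are assumed, and the comparison is with a site where nobody reacts to a serious event. The benefits are therefore upper bounds, and the true gain could be small.

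**Conclusion.** The point holds in a limited form. In the visible text, nothing holds the next infusion after an anaphylaxis or a pulmonary embolism or infarction, although this is a Phase 1/2 trial of an intravenous product with safety as a primary outcome. Adding such a step is an inexpensive safety improvement and corrects no analysis error.

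The size depends on rates that the documents do not give: a 27% to 47% chance of at least one triggering event at 1% to 2%, and 80% at 5%. Larger rates would enlarge every figure, but nothing in the documents supports choosing them. The calculation also assumes independent events recognised before the next infusion. The conclusion would fall if a page that is not visible already contains such a rule; a cross-reference in 4.7 would then be enough.

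A reader might infer that a formal two-event stopping rule is also needed. The documents do not support that. The threshold would be a judgement, and section 5 shows that the ethics committee approved the study, not that it reviews accumulating data. At 1% to 2% such a pause defers only 0.4 to 1.4 infusions on average.

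**What to change.** Amend section 4.7 to say that after any anaphylaxis, pulmonary embolism or pulmonary infarction within a stated window after infusion, no further patient is infused until three things are done:

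1. A named reviewer has assessed the event. This could be the principal investigator, with notification to the approving ethics committee.
2. The same review has covered any late serious events already seen in earlier patients.
3. The decision to continue, and its reason, has been recorded.

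The sponsor should choose the window and state it in 4.11.1, next to the immediate label.

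The change needs no extra visit, test or patient and leaves N = 31 alone. Its cost is the amendment itself and a short hold, which may follow a single chance event when the true rate is low. A second-event pause pending ethics-committee agreement is optional, and would need the committee to accept that role.
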